4 RESEARCH QUESTION/AIM(S)

Primary Aims:

Aim 1 - To validate the PHASES score in a UK population.

- Aim 2 To develop a new prediction model including all described predictors of risk.
- Aim 3 To report long-term risk of aneurysm rupture.

Secondary Aims:

Aim 4 – To develop risk models of aneurysm growth.

Aim 5 – To evaluate the efficacy of aneurysm screening regimens.

Aim 6 – To develop and evaluate new radiological predictors of aneurysm growth and rupture.

5 STUDY DESIGN and METHODS of DATA COLLECTION AND DATA ANALYIS

Data Collection – Baseline data – local neurosciences units Patients will be identified by members of the clinical care team and record:

- NHS number
- Name
- Date of birth
- Post code

These patients will be allocated a study number for pseudonymisation. This data will not be otherwise kept or used for other research purposes.

Further data will be collected from patient's case notes (either electronic or paper based as appropriate). A separate data definitions manual will be produced. All data collectors will be provided with a mandatory education module and correctly collect data from test cases before data collection.

The core covariates for each patient at time of diagnosis will be:

- Date of first diagnosis of aneurysm (date of first CTA/MRA/DSA or where not available date of first MDT or clinic appointment whichever is earlier)
- Date of inclusion in the study (date of first CTA/MRA/DSA or where not available date of first MDT or clinic appointment that lies within the unit's search period)
- Hypertension: a co-morbidity of hypertension or regular use of anti-hypertensive medication at time of diagnosis.
- Age: in years at time of diagnosis of aneurysm on angiographic imaging
- Gender:
- Site: anterior cerebral artery (including anterior communicating and pericallosal arteries), internal carotid (including bifurcation, ophthalmic, superior hypophyseal), MCA (including M1 segment and bifurcation), posterior communicating and posterior circulation (including vertebral, basilar, cerebellar and posterior cerebral arteries).
- Aneurysm size: the longest aneurysm dimension recorded to the nearest millimetre as described by the MDT discussion or where not available from the reporting radiologist at time of diagnosis or where not available from the clinic letter.
- Previous aneurysmal subarachnoid haemorrhage: confirmed diagnosis of aneurysmal SAH in the patient's medical history.

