There are multiple potential causes leading to underestimates of rupture risk. The magnitude of these will be estimated and corrected for. In view that all SAH events will be verified in clinical notes it is not expected that there will be any significant overestimation and consequently correction. Events may be missed due to migration. Any patients noted at time of baseline data collection to have emigrated will have this recorded and this will be used for censoring. Additionally, HES data will reveal any patients who have unregistered with their GP for emigration which will be used as a censoring event. Unfortunately, it is anticipated that not all patients will unregister on departure from the UK and therefore the observed emigration rate (that from the baseline data collection and HES data) will be subtracted from average national migration figures and this applied to the data.

Events may be missed due to miscoding. Aneurysmal SAH miscoded as:

1. Cerebral infarction (63.0-63.9 & I64.X)

Will be identified at one or more test sites by review of clinical notes to estimate any under-estimates due to miscoding and these estimates applied to the whole cohort.

In the event there are high rates of failed verification for the codes:

- 1. Intracerebral haemorrhage (including intraventricular haemorrhage (I61.0-61.9)
- 2. Subarachnoid haemorrhage (other and unspecified) (I60.8-60.9)
- 3. Non-traumatic subdural haemorrhage (I62.00-I62.02)
- 4. Traumatic subarachnoid haemorrhage (S06.6X0, S06.6X9A, S06.6X9, S06.6X8A)
- 5. I46.1 sudden cardiac death R98 unattended death
- 6. R96 other sudden death cause unknown
- 7. R98 unattended death

at some centres, then error estimates may be applied to the data from centres with robust code verification.

Additionally, at baseline data collection, any subsequent SAH events observed in the local notes will be recorded with their date, or date of last follow up. The SAH events observed during this follow up period will be compared to that for the similar period using HES data (after applying the above corrections), and the total risk estimates adjusted for any differences between these to give final 5 year risk estimates.

Discrimination will be assessed with the C statistic but is expected to be poor due to low event rates and therefore will be compared to the original PHASES data. Calibration will be assessed with calibration plots and Hosmer-Lemeshow tests.

Statistical analysis – Aim 2 - Additional prognostic factors

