7 SAMPLE AND RECRUITMENT

7.1 Eligibility Criteria

7.1.1 Inclusion criteria

- 1. Age 18 years or older.
- 2. Intracranial intradural unruptured aneurysm.
- 3. Confirmed on angiogram (CTA/MRA/DSA).

4. Diagnosis of UIA between January 2006-December 2020.

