7.3 Recruitment

7.3.1 Sample identification

Patient identification

Due to most UIAs being detected during investigation for other conditions, HES coding for outpatient appointments cannot reliably identify patients with intracranial aneurysms and a local review suggested this may lead to a large underestimate of cases.

Therefore, patients will be identified by the direct clinical care teams at adult tertiary neurosurgical units in the UK treating patients with UIAs. All patients will be eligible whether seen in the centre, scanned in the centre or only discussed with the centre at MDT or on-call. Therefore, more than one search method may be applicable. Search methodology may be adapted to suit local case note and radiology records. We would recommend sequentially performing the following searches:

- 1. Electronic keyword searches of clinic letters, discharge summaries and MDTs. These capture most patients but risk missing patients not formally discussed with neurosurgery.
- 2. Electronic searches of cranial CTA, MRA and DSA reports for the term "aneurysm" excluding "no aneurysm". These searches capture all patients at the parent hospital but may miss regional patients scanned in district hospitals.
- 3. Searches of on call referrals may capture any further conservatively managed UIAs.

In some units, paper records of MDT or vascular clinics may be searched where electronic systems are not in place. Additionally, some units maintain prospective neurovascular databases which could be used for patient identification.

To reduce selection bias all participating centres will produce a written search strategy for their unit and perform a search over a locally prespecified time period. This period will be within the range of 1 January 2006 – 31 December 2020 (representing the implementation of PACS and the present), but may be shorter. The date of inclusion will be the date of the first document to identify the patient in that locally prespecified date range. Where aneurysms were diagnosed before the study dates, the aneurysm will be marked as "known diagnosis" and the date of inclusion remains that of the first document in the study date range.

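### Date of inclusion is defined in two incompatible ways and no start of time at risk is named, so entry can be back-dated to before the unit knew the patient; the net bias is of unknown sign

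*Protocol*

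**What the plan says.** Two current passages define the same variable.

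- Protocol Section 5, baseline data, core covariates: "Date of inclusion in the study (date of first CTA/MRA/DSA or where not available date of first MDT or clinic appointment that lies within" (local search window follows). The MDT or clinic date is only a fallback for when there is no angiogram. It is also unclear whether the search-period condition applies to the angiogram or only to the fallback dates.
- Protocol Section 7.3.1: "The date of inclusion will be the date of the first document to identify the patient in that locally prespecified date range". For aneurysms diagnosed before the study dates, "the date of inclusion remains that of the first document in the study date range". Here a letter, a discharge summary or an on-call record can set the date.

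Four other statements bear on the point.

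- Searched sources include "Electronic keyword searches of clinic letters, discharge summaries and MDTs", and on-call referrals are a further search. Eligibility is broad: "All patients will be eligible whether seen in the centre, scanned in the centre or only discussed with the centre at MDT or on-call".
- Of the radiology-report search, Section 7.3.1 says: "These searches capture all patients at the parent hospital but may miss regional patients scanned in district hospitals".
- Section 7.1.1 requires an unruptured intradural aneurysm and "Diagnosis of UIA between January 2006-December 2020". Neither Section 7.1.1 nor 7.1.2 requires the unit to have known the patient before a rupture.
- Section 5, Aim 1 analysis, says of verified SAH events that "it is not expected that there will be any significant overestimation and consequently correction".

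Section 5 defines the end of follow-up, but nothing defines its start. The Aim 3 text speaks of time from diagnosis.

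**The concern.** In a retrospective cohort assembled from hospital records, the start date decides which events and which person-years count. If it can be set earlier than the moment the unit identified the patient, entry may depend on what happened in between.

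Take a patient with a CTA at a district hospital in 2012, no referral, a rupture in 2015, and a discharge summary from that admission as the unit's first document. Section 5 allows inclusion in 2012, and the 2015 rupture would count. Section 7.3.1 gives 2015, when the aneurysm is no longer unruptured, so there is no incident event. A similar patient who never bleeds and is never referred may not be found at all.

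The reverse case is a patient scanned elsewhere in 2012 and referred intact in 2015. Dating entry to 2012 credits three years in which, given how the patient was found, no rupture could have occurred.

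Absolute 5-year risk and calibration (Aim 1), the absolute risks from the new model (Aim 2) and the shape of the hazard over time (Aim 3) all depend on this date. Up to 30 units would extract it under two rules.

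**Working it through.** **Planning rate reproduced.** Inputs from Protocol Section 7.2.1: 51 ruptures, 1,692 patients, 4.1 years.

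- Rate = 51 / (1,692 × 4.1) = 51 / 6,937.2 = 0.735% per year.
- Patients for 60 events = 60 × 1,692 / 51 = 1,990.6. Person-years = 1,990.6 × 4.1 = 8,161.4. Both agree with the stated 1,990 and 8,161.
- Five-year risk at a constant rate = 1 − exp(−5 × 0.00735) = 3.6%.

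These figures are not in dispute. They serve only as a base for illustration.

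**Upward component.** Let k patients be identified only through their rupture and back-dated by t years. Rate = (60 + k) / (8,161 + k × t). The protocol gives neither k nor t, so both are assumed. With t = 2.5:

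- k = 1: 61 / 8,163.5 = 0.747% (ratio 1.016)
- k = 3: 63 / 8,168.5 = 0.771% (1.049)
- k = 6: 66 / 8,176 = 0.807% (1.098), five-year risk about 4.0%
- k = 12: 72 / 8,191 = 0.879% (1.196)

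Varying t from 1 to 5 years hardly matters: for k = 6 the ratio runs from 1.099 to 1.096.

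**Downward component.** Let a share g of the 1,990 patients be referred intact L years after an outside scan and be back-dated to it. Rate = 60 / (8,161 + g × 1,990 × L), with g and L again assumed.

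- g = 10%, L = 0.25: 60 / 8,210.75, ratio 0.994
- g = 20%, L = 0.5: 60 / 8,360, ratio 0.976
- g = 50%, L = 1: 60 / 9,156 = 0.655%, ratio 0.891, five-year risk about 3.2%

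**Both together, k = 6 and t = 2.5.**

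- With g = 10%, L = 0.25: 66 / (8,161 + 15 + 49.75) = 66 / 8,225.75 = 0.802%, ratio 1.09.
- With g = 50%, L = 1: 66 / (8,161 + 15 + 995) = 66 / 9,171 = 0.720%, ratio 0.98.

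The sign changes within the assumed ranges. Back-dating would be harmless only if ruptured and intact outside-scan patients were found equally completely, and nothing in the protocol secures that.

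**Whether planned checks would catch it.** Note review confirms that a bleed was aneurysmal; it does not show that the bleed brought the patient into the cohort. The comparison of locally recorded with HES-recorded SAH does not help either, because such an event can appear in both. The other Aim 1 corrections, for migration and miscoding, address missed events only.

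**The case against.** The strongest reply is that the troublesome case is narrow. It needs an outside angiogram, no referral or discussion, a rupture admission picked up by the discharge-summary search, and a unit that still treats the patient as having an unruptured aneurysm and back-dates entry. Section 3 says most patients with unruptured aneurysms are assessed in a neurosciences unit. The on-call search is aimed at conservatively managed aneurysms, and Section 7.1.1 already requires an unruptured aneurysm. A data definitions manual, mandatory training and test cases are planned, and each unit writes a search strategy.

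Much of this stands as a limit on size. It does not remove the gap. The requirement for an unruptured aneurysm carries no date, so it depends on the disputed inclusion date. Discharge summaries are searched without qualification. A manual cannot comply with two protocol rules that disagree.

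Three stronger readings are tempting but unsupported.

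- A reader might infer that rupture risk is overstated in all three primary aims. The same back-dating adds event-free time, so net inflation is not shown, and extra events do not by themselves fix the direction for discrimination.
- A reader might infer that the protocol admits intact district patients are missed. It says only that one of three sequential searches may miss them.
- A reader might infer that Section 5 starts follow-up at the scan. It lists the inclusion date as a data item, and no text makes it time zero. If time from diagnosis were used without delayed entry, back-dating could arise even with the inclusion-date conflict resolved, which is why the start of time at risk must be named as well.

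**Conclusion.** The contradiction between Sections 5 and 7.3.1 is established from current text, as is the absence of any stated start of time at risk. It is also established that the Section 5 wording, with the eligibility criteria as written, permits entry to be back-dated to before the unit knew the patient. This opens two biases of opposite sign, and the planned event verification would not reveal the upward one.

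The size is not established. The ratios of about 1.02 to 1.20 upward and 0.99 to 0.89 downward rest entirely on assumed values of k, t, g and L, applied to the protocol's planning base. They show that a handful of patients per 60 events is enough to matter, not that such patients exist in that number. The net direction is open. The point should be corrected because absolute risk is the main product of the study and one clear start date removes both distortions.

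**What to change.** Use one definition in Sections 5 and 7.3.1: the date of the first document created in the unit's search period by which the unit itself identified the patient as having an unruptured aneurysm. State that an earlier outside scan obtained later does not set this date. Taking the earliest document or scan of any origin while excluding rupture-identified patients would not do: it keeps the event-free time of late-referred patients and removes the matching events.

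Name this date as the start of time at risk, with delayed entry wherever time from diagnosis is the time axis, including for known diagnoses.

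Add to eligibility that this date must precede any SAH from the aneurysm. Patients first identified at or after the SAH presentation are then excluded from the rupture-rate and prediction analyses, and their number is reported.

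The cost is one definition, one eligibility sentence and matching text in the data manual. A few events and some person-time before identification are lost. Pilot cases already extracted need the date re-checked; Section 7.2.1 mentions 1,415 identified and 1,025 examined for ADPKD.

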- Population: European/North American, Finnish, Japanese (where race cannot be confirmed it will be assumed to be non-Finnish and non-Japanese on the basis that there is a low incidence of these populations in the UK and their presence would usually be considered noteworthy in a clinical note.

The additional desirable covariates at time of diagnosis will include:

- aspirin use any dose used >3* per week
- statin use any statin use >3* per week
- smoking history non-smoker, ex-smoker, current smoker
- Aneurysm multiplicity record number of intra-dural aneurysms the patient has (treated or untreated)
- Family history number of 1 first degree and second degree relatives with UIA/SAH
- History of Autosomal Dominant Polycystic Kidney Disease yes, no
- Aneurysm location subclassification ICA paraclinoid (ophthalmic and superior hypophyseal) ICA (PCom), ICA other (anterior choroidal and bifurcation), ACA ACOM, ACA pericallosal, MCA, Posterior (basilar termination), Posterior (SCA), Posterior (AICA) Posterior (PICA)
- Bleb or irregularity of aneurysm recorded as present or absent from radiology report only. If not mentioned in report assumed to be absent. If no radiology report available, then recorded as NA.
- New/known diagnosis: patients in whom the aneurysm was known prior to the search period will be recorded as known diagnosis and otherwise as new diagnosis.

Data collection – aneurysm rupture/censoring events – local neurosciences units

At the time of baseline data collection locally available follow up will be recorded which will include:

• Date of last follow-up

- Date of death (if applicable)
- Cause of death (if applicable)
- Date of SAH (if applicable)
- Location of aneurysm causing SAH (if applicable)
- Date of aneurysm treatment (if applicable)
- Reason for aneurysm treatment (if applicable)

This data will be used for quality control of subsequent HES searches.

Data collection - aneurysm rupture/censoring events - central HES ONS data

Upon collection of all baseline data, a search of the Hospital Episode Statistics (HES) and Office for National Statistics (ONS) databases using the patient's NHS numbers be conducted. The use of a HES and ONS search is designed to maximise the identification of rupture events which are not treated in neurosurgical unit as subarachnoid haemorrhage. It will thus identify events managed in a district general hospital or those who die pre-hospital.

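### For patients whose aneurysm was already known, covariates are dated at diagnosis, entry is at a later inclusion date and the start of follow-up is not stated, so the PHASES prediction and its risk window need not line up

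*Protocol*

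**What the plan says.** Section 5 (Data Collection – Baseline data) opens its core list with "The core covariates for each patient at time of diagnosis will be". Two items repeat that timing. Age is "Age: in years at time of diagnosis of aneurysm on angiographic imaging", and hypertension is "a co-morbidity of hypertension or regular use of anti-hypertensive medication at time of diagnosis".

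Two other core items are looser. Aneurysm size is taken "as described by the MDT discussion or where not available from the reporting radiologist at time of diagnosis or where not available from the clinic" correspondence, so only the second-choice source carries a date. SAH history reads "Previous aneurysmal subarachnoid haemorrhage: confirmed diagnosis of aneurysmal SAH in the patient's medical history", with no date of its own. For both, the link to diagnosis comes from the list heading. Smoking, aspirin, statin and irregularity stand under a second heading with the same timing.

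The same section collects two dates. One is "Date of first diagnosis of aneurysm (date of first CTA/MRA/DSA or where not available date of first MDT or clinic appointment whichever is earlier"). The other is a date of inclusion, which must fall within the unit's search period. The new/known field says that "patients in whom the aneurysm was known prior to the search period will be recorded as known diagnosis and otherwise as new diagnosis". Section 7.3.1 adds that, for aneurysms diagnosed before the study dates, "the date of inclusion remains that of the first document in the study date range". It also lets each unit search a shorter period than 2006–2020.

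Under Aim 1, Section 5 calculates the 5-year PHASES risk for everyone not censored before 5 years. Under Aim 3 it plans a model term for new against known diagnosis and a cumulative hazard plot on time from diagnosis. Last follow-up is defined; the start of follow-up is not.

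**The concern.** A validation of a 5-year risk score needs three things to refer to the same moment: the predictor values, the start of the 5-year window, and the point from which the patient is actually observed. For a newly diagnosed patient these normally coincide. For a known-diagnosis patient, the protocol dates the predictors at diagnosis and entry at a later document, and it does not say which of the two starts the window.

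At stake is the calibration result under Aim 1, where predicted 5-year risk is set against observed ruptures. The new-versus-known comparison under Aim 3 is also affected: if predictors are not brought up to date, that term takes in ageing, aneurysm growth and new comorbidity between diagnosis and inclusion, as well as any true difference between early and late risk.

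**Working it through.** No stated figure is challenged. The sample-size arithmetic in Section 7.2.1 is unaffected: 51/(1,692 × 4.1) = 0.735% per year, and 60 events at that rate need 8,161 patient-years, as stated.

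**Step 1: the dates for one known-diagnosis patient.**
- Predictors: diagnosis (Section 5; explicit for age and hypertension, by heading for the rest).
- Entry: first document in the unit's search range (Section 7.3.1).
- Start of follow-up: not stated.
- End of follow-up: earliest of HES search, GP deregistration, death or treatment (Section 5).

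**Step 2: how long the lag can be.** Inclusion criterion 4 (Section 7.1.1) requires diagnosis between January 2006 and December 2020, whereas Section 7.3.1 admits earlier diagnoses. Even with criterion 4 applied as written, a unit searching 2015–2020 could include a 2006 diagnosis: 2015 − 2006 = a lag of about 9 years.

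**Step 3: clock from inclusion.** With lag L, recorded age is too low by L years for that patient. Averaged over the cohort, the understatement is p × L, where p is the share of known cases. The protocol gives neither quantity, so both are assumptions:

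| Share p | L = 1 | L = 3 | L = 5 | L = 10 |
|---|---|---|---|---|
| 5% | 0.05 | 0.15 | 0.25 | 0.5 |
| 10% | 0.1 | 0.3 | 0.5 | 1.0 |
| 20% | 0.2 | 0.6 | 1.0 | 2.0 |
| 30% | 0.3 | 0.9 | 1.5 | 3.0 |

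(Years of age.) Turning this into PHASES points would need the score's age cut-off, which the protocol does not give. There is no basis at all for a figure on size, hypertension or SAH history.

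**Step 4: clock from diagnosis.** To be included, the aneurysm must still be unruptured (inclusion criterion 2) and untreated (exclusion criterion 5). Time between diagnosis and inclusion is therefore event-free by selection. The share of the 5-year window lost in this way is min(L, 5)/5:
- L = 1: 1/5 = 20%
- L = 3: 3/5 = 60%
- L of 5 or more: 100%, so the patient cannot contribute a rupture to the window at all.

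**Step 5: which clock is meant.** The Aim 3 plot uses time from diagnosis, which points one way. The inclusion date is collected separately and fixed for known cases, which points the other. The 15-year maximum follow-up expected under Aim 3 matches the 2006–2020 window, but does not decide the matter if pre-2006 diagnoses are barred.

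**Step 6: what can be recovered later.** Age at inclusion = age at diagnosis + (date of inclusion − date of first diagnosis); all three are core fields. Hypertension, size, irregularity, smoking and drug use at inclusion cannot be derived from diagnosis values.

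**The case against.** The strongest reply is that the protocol never says follow-up starts at inclusion. On the one time axis it names, time from diagnosis, diagnosis-time covariates match time zero. A Cox model on that axis with delayed entry at inclusion would be sound for Aims 2 and 3, and both dates it needs are collected. This stands, and it is why the point is an undefined origin together with the dating of covariates. It does not settle Aim 1: the calculation described there has no delayed entry, and on a diagnosis clock it counts the event-free time in Step 4.

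Four stronger readings are tempting, and the document does not support them.
- *Size and SAH history are fixed at the first scan.* Only the heading says so; the items themselves are undated or mixed, and the separate data definitions manual, which is not shown, may settle them.
- *Age information is lost.* It is not (Step 6).
- *PHASES will appear to under-predict.* Age can only rise and SAH history can only be added, so old profiles tend to score low. But known cases still eligible at inclusion have been selected for not having ruptured or been treated. Section 5 (Aim 2) expects many growing aneurysms to be treated, and Section 1 reports the belief that risk falls with time. The net direction is open.
- *Long lags will be common.* Criterion 4, applied as written, limits them to units whose search starts after 2006.

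An analysis plan could define time zero and derive age. It could not supply covariate values that sites were told to record at another date.

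**Conclusion.** The point holds in this form: predictors are tied to diagnosis, known-diagnosis patients enter later, the start of follow-up is unstated, and Aim 1 has no rule to align them. Either choice of clock leaves the 5-year prediction for these patients mismatched, through an old profile or through event-free time. New diagnoses are normally unaffected.

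The size and sign of the bias in Aim 1 calibration and in the Aim 3 new-versus-known term cannot be established from the protocol. The age range in Step 3 rests wholly on assumed shares and lags and is not an effect on calibration. The change is worth making because the covariates other than age are hard to recover once up to 30 units have abstracted their notes. Nothing here shows that the validation as a whole would fail.

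**What to change.** - State in Section 5 that time at risk starts at the date of inclusion.
- For known-diagnosis patients, record hypertension, smoking, aspirin, statin and previous SAH as known at inclusion. Take size and irregularity from the latest angiogram on or before that date.
- Derive age at inclusion from age at diagnosis plus the interval between the two collected dates. This avoids relying on date of birth, which belongs to the identifiable details that the coordinating centre deletes after upload (Sections 8.1 and 8.6).
- Keep the diagnosis values as separate fields, and score PHASES from the inclusion values.
- If Aim 3 keeps time from diagnosis as its axis, use delayed entry at inclusion.
- Reconcile inclusion criterion 4 with the admission of earlier diagnoses in Section 7.3.1.

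The cost is wording in Section 5 and the data definitions manual, plus some extra fields for known cases. Size at inclusion will sometimes fall back to an earlier scan, so the date of the scan used should be recorded.
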